7.2 Rationale

Most recent HIV cure efforts have focused on strategies to induce virus from latently infected cells during ART, thus leaving the cellular reservoir vulnerable to the host immune system, while ART prevents new cells from being infected. Unfortunately, such efforts have not demonstrated much activity. On the other hand, it has been documented for almost two decades that routine clinical vaccines can induce viral production from latently infected cells, even during ART, and that these levels of induction are much higher than those seen by recently described interventions (e.g. histone deacetylase inhibitors (HDACi), IL-7, disulfiram). Therefore, we propose a RCT with cross-over to determine how two commonly used vaccines (Influenza and Pneumococcus) can stimulate the immune system and induce HIV transcription. In preliminary data, these vaccines demonstrate a higher cell associated HIV RNA transcriptional response even 30 days after vaccination than the HDACi Vorinostat; see Figure 2. In this proposal, we will use a much safer method (vaccination with Influenza and Pneumococcus) and observe timepoints much closer to the time of vaccination to tease out how immune stimulation perturbs the HIV DNA reservoir suppressed by ART.

Rationale for measuring total and replication competent HIV DNA

Currently, much emphasis has been placed on the kick portion of the kick-and-kill HIV cure strategy; however, only modest benefit has been seen with kick interventions and almost none with the killing of infected cells- at least with the current measurements in circulating blood [7, 9-13]. In this study, we will use clinically available influenza and pneumococcus vaccines to stimulate the HIV reservoir and stimulate the immune response. In the prior Spanish Study, described in the Background, it was observed that HIV-specific immune response was enhanced during the 'kick' of the reservoir in the blood after a clinical vaccine. This study did not measure HIV DNA levels or replication competent proviral levels; therefore, we do not know if this HIV-specific immune stimulation had an impact on the HIV reservoir in circulating blood cells. Therefore, in the proposed RCT, we will assess both total HIV DNA levels and replication competent provirus (using an "inducible RNA assay" [95]) among the five participants with the highest cell associated HIV RNA response to the vaccine intervention.

Microbiome Composition

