7.3 Major Hypotheses

(All hypotheses are presented “under the alternative”)

Primary Hypothesis:

On average, participants will have a higher absolute increase in levels of cell-associated HIV RNA transcription in CD4⁺ T-cells seven days after receiving either Pneumococcal or Influenza vaccinations, when compared to seven days after receiving placebo.

Secondary Hypotheses:

- Among the five participants with the largest increases in cell-associated HIV RNA in CD4⁺ T-cells following active vaccination (maximum across all observed time-points), we will deep sequence cell-associated HIV RNA and DNA populations at 0, 2, 4, 7, 14 and 30 days. We hypothesize that active vaccines will *non-selectively* activate cellular transcription of HIV, as evaluated by panmixis tests between sequences of HIV DNA and RNA populations at these sampled timepoints.
- On average, participants will have a greater absolute maximum decrease in levels of total CD4⁺ T-cell-associated HIV DNA measured 2-30 days after receiving either Pneumococcal or Influenza vaccinations, when compared to 2-30 days after receiving placebo.
- Among the five participants with the largest increases in cell-associated HIV RNA in CD4⁺ T-cells following active vaccination (maximum across all observed time-points), we will perform inducible RNA assay. We hypothesize that these five participants will have lower levels of replication competent proviruses 30 days after active vaccination, as compared to their levels of replication competent proviruses sampled before this vaccination.
- Participants will have a greater absolute maximum increase in levels of (a) inflammatory cytokines, (b) T-cell activation and proliferation, (c) HIV-specific immune responses, and (d) vaccine-specific immune responses over the 30 days of observation after receiving either active vaccination, when compared to maximum measures taken over the 30 days of observation after receiving placebo.

- Levels of non-antigen specific immune stimulation (cytokines and general T-cell activation) and vaccine-specific immune responses will be positively associated with increased CD4⁺ T-cell-associated HIV RNA transcription and negatively associated with lower levels of HIV DNA, over the 30 days of observation after receiving either Pneumococcal or Influenza vaccinations.

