12.2 Laboratory Evaluations

All laboratory procedures will be conducted in accordance with Good Clinical Laboratory Practices (GCLP) according to the [DAIDS guidelines](#).

A urine pregnancy test will be performed at screening in women who can become pregnant and will be repeated only if pregnancy is suspected.

A rapid HIV test will be performed if no documentation of previous HIV infection is provided.

Table 3 is a summary table of study assays, methods and time points.

	Measurements	Methods	Sample	Sampled Time-points (Days)
Virologic (Aims 1+2)	Cell-associated HIV RNA levels	(dd)PCR	PBMC (CD4+)	
	HIV DNA levels (pol and 2-LTR)	(dd)PCR	PBMC (CD4+)	0, 2, 4, 7, 14, 30 after each injection
	Cell-free HIV RNA levels	SCA	Blood plasma	
	Cell-associated HIV RNA diversity*	env NGS	PBMC (CD4+)	0 and time point with highest cell associated HIV RNA level after the active vaccination
	Cell-associated HIV DNA diversity*	env NGS	PBMC (CD4+)	
	Replication competent HIV levels*	DNA Inducible RNA assay	PBMC (CD4+)	0 and 30 after each active vaccine
Immunologic	Soluble inflammation markers	ELISA	Blood plasma	0, 2, 4, 7, 14, 30 after each injection

(Aim 3)	Vaccine-specific response	ELISA	Blood plasma	
	Cellular inflammation markers	Flow	PBMC	
	HIV-specific T-cell response	Flow ICC	PBMC	
Incidental stimulation	Microbiome Composition	r16s Sequencing	Stool	Day 0
	HHV quantification	qRT-PCR	GS	0, 14, 30 after each injection
	Incident Illness surveys	Survey	--	

Legend: ddPCR: digital droplet PCR, SCA: single copy assay, PBMC: peripheral blood mononuclear cells, ELISA: enzyme linked immunoassay, Flow: flow cytometry, ICC: intracellular cytokine staining, qRT-PCR: quantitative real time PCR. GS: genital secretion. *The 5 participants with the highest sum levels of cell-associated HIV RNA within the 30 days (five measures) following both active vaccinations will undergo these assessments. These same 5 participants will be used for both of these analyses.

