15.2 Study Endpoints

15.2.1 Primary Endpoint

Average change in level of CD4+ T-cell-associated HIV RNA transcription from baseline to 7 days after each injection.

15.2.2 Secondary Endpoints:

1. Average change in level of CD4+ T-cell-associated HIV RNA transcription from baseline to 2, 4, 14 and 30 days after each injection.
2. Average change in levels of HIV DNA from baseline to 2, 4, 7, 14 and 30 days after each injection.
3. Determine selective vs. nonselective HIV RNA production from HIV DNA (by next generation sequencing and panmixis tests) among the five participants with the highest levels of cell associated HIV RNA following active vaccination.
4. Average change in levels of immune activation (soluble and cellular markers) from baseline to 2, 4, 7, 14 and 30 days after each injection.
5. Average change in levels of replication competent HIV DNA (by inducible RNA assay) among the five participants with the highest levels of cell associated HIV RNA following active vaccination.
6. Average change in levels of HIV specific T-cell immune response from baseline to 30 days after each injection.
7. Stimulation of HIV transcription by incidental illness, human herpesviruses replication and microbial translocation over the course of the study.
8. Possible immunomodulatory effect of microbiome composition
9. Vaccine administration will be safe for all included participants.

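### The five participants for sequencing and the inducible RNA assay are chosen by largest increase in 7.3 but by summed raw levels in Table 3, and the sequencing days also differ

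*Combined protocol and SAP*

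**What the plan says.** Four places in the protocol describe the same five people.

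- Section 7.3 (secondary hypotheses on sequencing and on replication-competent provirus) takes the "five participants with the largest increases in cell-associated HIV RNA" in CD4+ T-cells after active vaccination, using the maximum over the observed time points.
- The Table 3 legend (section 12.2) takes "The 5 participants with the highest sum levels of cell-associated HIV RNA within the 30 days (five measures) following both active vaccinations", and says that one set of five serves both assays.
- Section 15.2.2, items 3 and 5, runs the two analyses "among the five participants with the highest levels of cell associated HIV RNA following active vaccination".
- Section 7.2 runs the provirus assay "among the five participants with the highest cell associated HIV RNA response to the vaccine intervention".

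The sequencing schedule is also given twice. In 7.3: "we will deep sequence cell-associated HIV RNA and DNA populations at 0, 2, 4, 7, 14 and 30 days". In Table 3: "0 and time point with highest cell associated HIV RNA level after the active vaccination". For the inducible RNA assay, Table 3 has "0 and 30 after each active vaccine", which agrees with 7.3 on the days.

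No section says which version governs. Section 15.8.2 refers further analyses to a Statistical Analysis Plan whose text is not in the document reviewed.

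**The concern.** An increase and a level are different quantities. The five post-injection measures in a cycle are days 2, 4, 7, 14 and 30, so a sum over five measures neither contains nor subtracts day 0. A person whose transcription is always high scores well on that sum whether or not the vaccine did anything. Sections 7.2 and 7.3 want people whose reservoir responded: the hypotheses are that vaccination activates transcription non-selectively, and that replication-competent provirus falls after it. If the five did not respond, neither question is properly tested.

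Aim 1b and the provirus part of Aim 2 rest on these five people alone. Both rules also require knowing which cycles were active. If the rule is still open at unblinding, it would be settled with RNA results and treatment codes both in view.

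**Working it through.** **1. The rules side by side**

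| | 7.3 | Table 3 legend |
|---|---|---|
| Quantity | increase | raw level |
| Summary over visits | maximum | sum of five measures |
| Cycles | not specified | both active cycles |
| Day 0 | implied reference | not used |
| Sequencing days | 0, 2, 4, 7, 14, 30 | 0 and peak day |

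Section 15.2.2 speaks of levels and so leans to Table 3; 7.2 speaks of response and so leans to 7.3. Neither gives a metric. This is therefore not a single slip of wording. Section 7.3 also leaves open, for this selection, whether an increase is absolute (as in its primary hypothesis) or fold (as in the preliminary data of 7.1.2).

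**2. When a non-responder outranks a responder under Table 3**

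Let a responder have baseline B and rise by d at k of the five visits in both active cycles. The Table 3 sum is 10B + 2kd. A flat non-responder at B + x has the sum 10B + 10x. The non-responder ranks higher when 10x > 2kd, that is, x > kd/5.

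For an illustrative d, take the figures in 15.4: SD 625 and a detectable difference of 253 with 50 evaluable participants. A paired t-test (two-sided 0.05, 80% power, n = 50, SD 625) gives 252.6, which reproduces the 253. Assume that changes are normal with mean 253 and SD 625.

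- Ranking one change per person: the fifth-largest of 50 standard normal values averages about 1.33, so d is about 253 + 1.33 × 625 = 1,084, and with k = 1 the threshold is x of about 1,084/5 = 217.
- Section 7.3 ranks a maximum, however. Over ten post-injection measures per person (five visits, two active cycles), simulation puts the fifth-largest maximum at about 1,360 (correlation 0.9 between measures) to 1,620 (correlation 0.5). With k = 1 the threshold is then about 1,360/5 = 272 to 1,620/5 = 324 copies per 10^6 CD4 T-cells.
- If the rise lasts all five visits (k = 5), the threshold is d itself, about 1,360 to 1,620.

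The threshold therefore depends heavily on how long the rise lasts. Whether a baseline gap of a few hundred copies is common depends on the between-person spread of RNA levels, which the documents do not give.

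**3. How many people the two rules share (assumed inputs)**

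Simulated cohorts of 50 with two active cycles, comparing Table 3 with the largest absolute increase:

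- Response unrelated to baseline: 0.5 to 2.1 of 5 shared (chance alone gives 5 × 5/50 = 0.5).
- Response proportional to baseline: roughly 3 to 4.2 of 5 shared.

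True responders among the five, if 30% of participants respond in proportion to baseline (chance gives 5 × 0.30 = 1.5):

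| Response | Table 3 | Absolute increase |
|---|---|---|
| Two-fold, transient | 1.7–2.3 | 2.2–3.3 |
| Four-fold, sustained | 3.7–4.5 | 4.1–4.9 |

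**4. Samples to be sequenced**

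Five people, with RNA and DNA each sequenced:

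- 7.3, both active cycles: 5 × 2 cycles × 6 days × 2 = 120; one cycle: 60.
- Table 3, both active cycles: 5 × 2 cycles × 2 days × 2 = 40; one cycle: 20.

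The ratio is three to one either way and needs no assumption about the data.

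**The case against.** The strongest reply is that little is lost. Unblinding comes at about 44–48 months, after all follow-up (15.5, 15.8.2), so selection is probably one central, late step. Cell-associated RNA is measured in everyone at every visit (Table 3), and all PBMC are stored (12.2.3). Unless stored cells run out, the choice can still be made correctly. This stands, and it limits the harm. A reader might infer that different staff would send different samples to the laboratory during the trial; the documents do not support that picture.

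A reader might also infer from the low-overlap scenario that the two rules would usually pick different people. That cannot be shown. Baseline spread, responder share, size of response and noise are all assumed, and the 253 is a detectable difference from placebo, not an expected rise. Section 7.2 reports a response even 30 days after vaccination, so the sustained case, in which the rules agree best, deserves as much weight as the transient one.

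Table 1 marks RNA and DNA sequencing at every visit, which may look like a third conflicting schedule. It has no separate row for RNA or DNA levels, although these are measured at every visit, so those rows may simply be loosely labelled sampling rows. They are not counted here.

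Finally, Table 3 states visits and vaccines more fully than 7.3, and an increase rule has its own weakness: it partly favours people whose day-0 value is low by chance. Both points are fair. They bear on how the rule is written; they do not remove the contradiction or make a raw level a measure of response.

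**Conclusion.** The inconsistency is certain from the text: two selection rules for the same five people, and two lists of sequencing days. It also follows from the definitions that Table 3, as written, can select people with high baseline transcription and little response, against the stated purpose.

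How often the two rules would differ in practice is not determined. The range of roughly 0.5 to 4.2 shared people out of five rests on assumed inputs, with the closest agreement when the response is large, sustained and proportional to baseline.

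The reach is narrow. A reader might take this as a threat to the trial's main result, but the primary endpoint uses all participants and neither it nor the sample size is touched. Total HIV DNA, the other part of Aim 2, is measured in everyone. What is affected is the sequencing analysis and the inducible RNA analysis, each in five people. The latter compares day 30 with day 0 in active cycles only, without a placebo reference, so it is descriptive under either rule. The point should be corrected, at low cost, before unblinding. The unseen Statistical Analysis Plan may already settle the rule; these sections would still need to match it.

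**What to change.** Before unblinding:

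1. Put one baseline-corrected rule in 7.3, the Table 3 legend and 15.2.2 (items 3 and 5): the five participants with the largest maximum increase over that cycle's own day 0, across days 2–30 of the active cycles.
2. The sponsor should fix whether the increase is absolute or fold. Absolute change matches the primary hypothesis in 7.3 but still partly favours high baselines. Fold change removes that, but leans more on day-0 values that are low by chance: in simulations with no true response and assumed inputs, the chosen people's day-0 value was low by 38–56% under fold change and 19–26% under absolute change.
3. State whether one or both active cycles are assayed. Table 3's inducible RNA row already covers each active vaccine; the sequencing wording does not settle it.
4. Use one list of sequencing days in 7.3 and Table 3.
5. Report the inducible RNA result as descriptive.
6. If the Statistical Analysis Plan cited in 15.8.2 already fixes a baseline-corrected rule, make these sections match it.

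Cost: wording only for the rule, with no new visits or participants. Keeping Table 3's two sequencing days adds no laboratory work. Adopting 7.3's six days means 80 more samples sequenced for both active cycles (120 − 40), or 40 more for one (60 − 20).

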12.2.1 Specimen Preparation, Handling and Shipping

All laboratory procedures related to specimen preparation, handling and shipping will be conducted in accordance with Refer to DAIDS Policy Requirements for Laboratories in Clinical Trials, Guidelines for Good Clinical Laboratory Practice Standards and DAIDS Manual of Operational Procedures. The following AVRC Site SOPs are listed below and attached in the Appendix.

- Laboratory SOP “Transporting Specimens within and outside UCSD” (Appendix E)
- Laboratory SOP “Quality Management Plan” (Appendix F)

12.2.2 Biohazard Containment

Transmission of HIV and other blood borne pathogens can occur through contact with contaminated needles, blood, and blood products. Appropriate blood and secretion precautions will be employed by all personnel in the collection of clinical samples and the shipping and handling of all clinical samples and isolates for this study, as currently recommended by the Centers for Disease Control and Prevention in the United States, the WHO internationally and the National Institutes of Health.

All protocol specimens will be shipped using packaging that meets requirements specified by the International Air Transport Association Dangerous Goods Regulations for UN 3373, Biological Substance, Category B, and Packing Instruction 650. Culture isolates, if obtained in this study, are to be shipped as specified for UN 2814 Category A Infectious Substances. All infectious specimens will be transported using packaging mandated in the Federal Code of Regulations, CDC 42 CFR Part 72. Please also refer to individual carrier guidelines, e.g., FedEx, Airborne, for specific instructions.

12.2.3 Total Blood Volume

Participants will have blood drawn at each visit. Approximately 50 or 60 mL of blood will be drawn for the following tests and storage for future research:

- CD4+/CD8+ T-cell Count (3 mL of blood).
- HIV-1 RNA (Viral Load) (6 mL of blood).
- Routine blood chemistry tests, a comprehensive metabolic panel and a complete blood count will be performed to determine overall health at baseline, day 14 and day 30 (we will collect 10 mL of additional blood).
- Blood will be collected for storage (6 mL of blood plasma and all PBMC). Some of the blood will be stored to perform future HIV testing and human genetic testing as well as to assess adherence to ART. Blood will be stored with the usual protectors of identity. The results of these tests will not be shared with the participant since these tests are not used for clinical management of their HIV.

Participants will have approximately 50 or 60 mL of blood drawn at a time with an approximate total of 990 ml (4.5 cups) drawn for this study over the course of 8 months.

12.3 Schedule of Procedures/Evaluations

See Table 1 (page 12) for schedule of evaluations.

12.3.1 Screening

At screening a survey will establish inclusion and exclusion criteria. A screening CRF checklist and a screening survey will be completed by nursing staff. The screening visit will involve a discussion of vaccination history and medical history relevant to the inclusion and exclusion criteria. In addition documentation of plasma HIV-1 RNA and CD4+ T-cell counts will be recorded in the source documents and electronic CRF. A urine pregnancy test will be performed at screening in women who can become pregnant and will be repeated only if pregnancy is suspected.

Written informed consent explained by trained clinical staff will occur before starting screening procedures. The baseline visit (study entry) and administration of the vaccine or vaccine-placebo intervention will be performed within 30 days of the screening visit.

12.3.2 Enrollment

If the participant meets eligibility criteria, a participant identification number (PID) will be assigned to each individual screened and determined to be eligible for the study. PIDs will include a site code and three-digit extension. PIDs may not be reassigned even if the individual fails to enter the study. The PID must be included on every CRF and blood sample. The site must maintain a master list of PIDs in a central location. Participant registration and inclusion/exclusion CRF must be completed. Study entry will occur within 30 days of screening.

The study statistician will provide a randomization list to the pharmacist prior to study start. This list will be used in consecutive order to randomize participants at the time of enrolment.

12.3.3 HIV Counseling and Testing

No HIV testing will occur, as participants must have documented HIV-1 infection more than 365 days prior to enrollment (HIV antibody or viral load positive). Participants are required to be on ART for at least 48 weeks. Counseling can be provided to any participant.

12.3.4 Follow-up

12.3.4.1: Baseline assessments [Day 0 of each cycle]

(These visits will last about 1.5 hours): At study entry the subject should complete all assessments and clinical evaluations with blood sample for banking. Antibody levels for each tested vaccine, cell-associated HIV RNA levels in blood plasma and HIV DNA levels in PBMC should be measured. An optional genital secretion and an optional stool sample will also be collected at baseline assessments. Refusal to provide genital secretion and/or stool sample will not result in termination from the study.

Placebo or vaccine injections: Will be performed by study nursing personnel based on stratification delivered by study pharmacist at baseline.

12.3.4.2 On study evaluations post-vaccination [Days 2, 4, 7, 14 & 30]

(These visits will last about 1 hour): At the time of each injection and five sampling time points afterwards, the following should be measured: cell-associated and cell-free HIV RNA levels, HIV DNA levels, vaccine-specific antibody levels, soluble and cellular inflammatory and proliferation markers, and HIV specific T-cell response. Genital secretion samples will be collection at post-vaccination evaluations 14 and 30 only.

12.3.5 Early Termination Visit

If a subject is unable to complete all of the study visits, they will be asked to return to the clinic to for a study discontinuation visit. The following procedures will be performed:

- brief physical exam and concomitant medication questionnaire
- blood drawn for routine safety tests to check your blood count, liver and kidney function, CD4+cell count, viral load and storage for future testing
- survey about recent illnesses and symptoms
- optional collection of genital secretion

CRITERIA FOR EARLY TERMINATION.

- Active drug or alcohol use or dependence that, in the opinion of the investigator, would interfere with adherence to study requirements.
- The subject becomes pregnant during the course of the study.
- Failure by the subject to attend scheduled clinic visits may result in discontinuation.
- Request by the subject to withdraw from the study.
- The participant's HIV therapy fails.

- Request of the primary care provider if s/he thinks the study is no longer in the best interest of the subject.
- Clinical reasons believed life threatening by the physician.
- Subject judged by the investigator to be at significant risk of failing to comply with the provisions of the protocol as to cause harm to self or seriously interfere with the validity of the study results.

